### 5.4. Other Considerations for Data Analyses and Data Handling Conventions

Other considerations for data analyses and data handling conventions are outlined in the appendices:

Section	Component
12.3	Appendix 3: Assessment Windows
12.4	Appendix 4: Study Phases and Treatment Emergent Adverse Events
12.5	Appendix 5: Data Display Standards & Handling Conventions
12.6	Appendix 6: Derived and Transformed Data
12.7	Appendix 7: Reporting Standards for Missing Data
12.8	Appendix 8: Values of Potential Clinical Importance

## **6. STUDY POPULATION ANALYSES**

### **6.1. Overview of Planned Study Population Analyses**

The study population analyses will be based on the Safety population, unless otherwise specified.

Study population analyses including analyses of participant's disposition, protocol deviations, demographic and baseline characteristics, prior and concomitant medications, and exposure will be based on GSK Core Data Standards. Details of the planned displays are presented in [Appendix 10: List of Data Displays](#).

Data from the standard of care arm will be pooled for the analysis, except for the display of Summary of Participant Disposition at Each Study Epoch, which will be displayed by cohort.

## **7. EFFICACY ANALYSES**

### **7.1. Primary Efficacy Analyses**

#### **7.1.1. Endpoint / Variables**

Rate of change in  $\log_{10}$  colony forming units ( $\log_{10}$ CFU) per ml direct respiratory sputum samples over the period baseline to Day 14 (EBA CFU0-14).

#### **7.1.2. Summary Measure**

Mean daily rate of change in  $\log_{10}$ CFU for each treatment group.

#### **7.1.3. Population of Interest**

The primary efficacy analyses will be based on the efficacy population, unless otherwise specified.

#### **7.1.4. Strategy for Intercurrent (Post-Randomization) Events**

The primary treatment effect to be estimated will be the while on treatment effect of initial randomised treatment.

All recorded data up to the time of study withdrawal will be included in the analysis, regardless of discontinuation of study medication.

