## 8. DISCONTINUATION CRITERIA

If study treatment/investigational product is interrupted or stopped this does not automatically result in the participant being withdrawn from the study. The investigator will make all effort to retain the patient in the study, provided the participant continues to provide their consent, and to complete and record all scheduled safety assessments required by the protocol. For the avoidance of all doubt: this does not prejudice the rights of the investigator and study participants under ICH GCP and under applicable laws. The study participant retains the right to withdraw consent at any time for any reason. The investigator also retains the right to withdraw the patients from the study if in the investigator's judgement, withdrawal is judged clinically necessary to protect a participant's safety.

If this results in the patient being placed on standard of care (i.e. Rifafour e-275 or equivalent generic alternative), then all assessments relevant to Rifafour e-275 (or equivalent generic alternative) will be performed as directed by the protocol (for

example, GSK3036656 pharmacokinetic assessments are not required, since the participant is not being dosed with GSK3036656).

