## 4. ANALYSIS POPULATIONS

Population	Definition / Criteria	Analyses Evaluated
Screened	
 
• All participants who were screened for eligibility
 
	
 
• Study Population
 

Randomized	
 
• All participants who were randomly assigned to treatment in the study.
 
• This population will be based on the treatment the participant was randomized to.
 
• Any participant who receives a treatment randomization number will be considered to have been randomized.
 
	
 
• Study Population
 

Enrolled	
 
• All participants who passed screening and entered the study. Included are run-in failures and randomized participants.
 
• Note: screening failures (who never passed screening even if rescreened) and participants screened but never enrolled into the study (Reserve, Not Used) are excluded from the Enrolled population as they did not enter the study.
 
	
 
• Study Population
 

Safety	
 
• All randomized participants who received at least one dose of study treatment.
 
	
 
• Safety
 

Population	Definition / Criteria	Analyses Evaluated
	
 
• Participants will be analysed according to the treatment they actually received.
 
• Note: Participants who were not randomized but received at least one dose of study treatment should be listed.
 
	
Efficacy	
 
• All participants in the safety population who provided at least two evaluable overnight sputum samples.
 
• This population will be based on the treatment the participant was randomized to.
 
	
 
• Efficacy
 

Pharmacokinetic (PK)	
 
• Participants in the safety population who received at least one dose of GSK3036656 and have at least one evaluable PK sample.
 
• Participants will be analysed according to the treatment actually received.
 
	
 
• PK
 

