For participants who receive the incorrect treatment (i.e. a different treatment to what they were randomised to), the participants will be assigned to the actual treatment groups if they received that treatment for more than 50% of their doses.

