
Sensitivity and Supportive Analyses
 
 
A sensitivity analysis will be performed (Model 1 only) excluding participants who withdraw from the study before Day 10 and/or who were replaced during the study.
 
Additional covariates (see Section 5.3) will be investigated in an exploratory manner using a mixed model repeated measures analysis. Each covariate will be investigated separately utilizing the model described for the primary endpoint. First the primary endpoint model will be fitted but including the covariate of interest and then the primary endpoint model will be fitted including both the covariate and treatment-by-covariate interaction.
 

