### **7.2.4. Strategy for Intercurrent (Post-Randomization) Events**

The treatment effect to be estimated will be the while on treatment effect of initial randomised treatment.

All applicable recorded data up to the time of study withdrawal will be included in the analysis, regardless of discontinuation of study medication.

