#### 9.1.4. Strategy for Intercurrent (Post-Randomization) Events

- The treatment effect to be estimated will be the while on treatment effect of actual received treatment.
- All applicable recorded data up to the time of the intercurrent event will be included in the analysis.

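### SAP 7.1.4 and 7.2.4 declare a while-on-treatment effect but keep counts taken after study medication stops, so standard-of-care killing could be credited to GSK3036656

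*SAP*

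**What the plan says.** For the primary endpoint, SAP 7.1.4 says: "The primary treatment effect to be estimated will be the while on treatment effect of initial randomised treatment". Its next sentence sets the data rule: "All recorded data up to the time of study withdrawal will be included in the analysis, regardless of discontinuation of study medication". SAP 7.2.4 repeats both for the secondary CFU and TTP endpoints, with one added word: "All applicable recorded data up to the time of study withdrawal will be included in the analysis, regardless of discontinuation of study medication". For PK, SAP 9.1.4 also names a while-on-treatment effect (of the treatment received) but ends the data earlier: "All applicable recorded data up to the time of the intercurrent event will be included in the analysis".

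Protocol Section 8 says that stopping study treatment is not in itself study withdrawal. If the participant is then placed on standard of care, "then all assessments relevant to Rifafour e-275 (or equivalent generic alternative) will be performed as directed by the protocol".

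SAP Section 4 says of the efficacy population: "This population will be based on the treatment the participant was randomized to". A note under the same table covers participants who receive a treatment other than the randomised one: "the participants will be assigned to the actual treatment groups if they received that treatment for more than 50% of their doses". The only sensitivity analysis that drops participants (SAP 7.1.5.1, Model 1 only) is one "excluding participants who withdraw from the study before Day 10 and/or who were replaced during the study".

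**The concern.** A while-on-treatment effect uses outcomes observed while the participant takes the assigned drug. Keeping data whether or not the drug has been stopped is a treatment-policy rule. The two sentences therefore define different quantities.

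The difference matters because the primary objective is the bactericidal activity of GSK3036656 itself. If a participant moves to four-drug therapy at mid-course and still gives sputum, the later counts reflect that therapy but are analysed in the GSK3036656 arm. If standard of care kills faster than the GSK3036656 dose, activity is overstated. If a participant stops and takes nothing, activity is probably understated. Under SAP 3.1 the same analysis may be run mid-study to guide dosing of later cohorts, so a distorted slope could reach dose selection. Arms may now be as small as nine.

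**Working it through.** **Can the data arise, and does anything remove them?**

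1. Protocol Section 8 allows the stop, the move to Rifafour and continued follow-up. Appendix 7 (liver) also stops treatment and keeps the participant in the study.
2. Sputum after a switch is inferred, not stated. Section 8's one example of an assessment no longer required is GSK3036656 PK. The Schedule of Activities restricts PK sampling to GSK3036656 participants but schedules overnight sputum without regard to arm.
3. The efficacy population is grouped as randomised, so these counts enter the GSK3036656 slope.
4. The sensitivity analysis depends on study withdrawal before Day 10 or on replacement. A switcher who stays and is not replaced is kept.
5. If the 50%-of-doses note covers switchers, a switch after Day 6 gives 8/14 = 57% Rifafour doses. The participant moves to the standard-of-care group and takes the GSK3036656-period counts along. A switch after Day 7 gives 7/14 = 50%, which is not more than half, so the participant stays in the GSK3036656 arm.

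**Inputs.** Sampling days are baseline (Day 0) and Days 1, 2, 3, 4, 6, 8, 10, 12 and 14 (Schedule of Activities, footnote L). Arm sizes 9 and 15, SD 0.15, the observed 5 mg SD of 0.067 and the slope -0.06 come from Protocol 10.1. Assumed: one switcher, a GSK3036656 slope g from -0.03 to -0.06, a Rifafour slope s from -0.10 to -0.20, and the switch day k.

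**Plan's own figure.** The plan gives none for switching. Its chance of about 90% of a negative arm mean at n = 9 reproduces as Φ(0.06 × √9 / 0.15) = Φ(1.2) = 88.5%. The planning standard error is 0.15/√9 = 0.050.

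**Formula.** The mean sampling day is 60/10 = 6 and the sum of squared deviations is 210. A participant with slope g up to Day k and s afterwards has least-squares slope g + (s - g)·w, where w = Σ(t - 6)·max(t - k, 0)/210. One such participant among n shifts the arm slope by (s - g)·w/n.

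**Middle case** (g = -0.06, s = -0.15, k = 6):
- w = 120/210 = 0.571, so the participant's slope is -0.06 - 0.09 × 0.571 = -0.1114.
- At n = 9 the shift is -0.0514/9 = -0.0057/day, or 9.5% of the slope. At n = 15 it is -0.0034/day, or 5.7%.
- Against the standard error of a nine-person arm: 0.0057/0.050 = 11%, or 0.0057/(0.067/√9) = 0.0057/0.0223 = 26%.

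**Range at n = 9, one switcher**

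| Switch after | w | Low (g -0.06, s -0.10) | High (g -0.03, s -0.20) |
|---|---|---|---|
| Day 4 | 160/210 | 5.6% | 48.0% |
| Day 7 | 100/210 | 3.5% | 30.0% |
| Day 8 | 80/210 | 2.8% | 24.0% |
| Day 10 | 44/210 | 1.6% | 13.2% |

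**Stopping without standard of care, counts then flat.** The arm slope is understated by w/9: 8.5% (Day 4), 6.3% (Day 6) or 4.2% (Day 8).

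**Model checks.** Generalised least squares with a random intercept and AR(1) correlation from 0 to 0.8 gives 9.5% to 10.3% in the middle case. In a simulation with one Day 5 switcher in nine (g = -0.06, s = -0.15), all data gave -0.0660 and data cut at the switch gave -0.0594.

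**The case against.** The strongest reply is that the route is narrow and the effect small.

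- **Route.** Section 8 says retained participants complete their scheduled safety assessments and does not name sputum. QTc stops are study withdrawals (Protocol 8.1.2). Protocol 3.3.1 describes haemoglobin and neutrophil stops as study withdrawal, whereas 8.1.3 only discontinues the product. On the first reading, liver stops are the only laboratory or ECG trigger that expressly keeps a participant in the study off drug. This narrows the route but does not close it. The SAP clause about discontinuation has an effect only if efficacy data exist after stopping.
- **PK contrast.** SAP 9.1.4 refers to received treatment, not randomised treatment, and PK is not needed after a switch. So it is supporting evidence only; the mismatch within 7.1.4 and 7.2.4 does not depend on it.
- **Legitimate choice.** The data rule is explicit and reproducible, and analysing all data is a defensible strategy. That is true, but it is then not a while-on-treatment analysis and does not isolate GSK3036656.
- **The 50% note.** It is written for participants given the wrong treatment, and a protocol-directed switch is not naturally that. The note may well not apply, but the SAP does not say so.
- **Size.** The 48% case uses assumed extremes and is 0.0144/day: -0.030 becomes -0.044, still short of the protocol's -0.06 mark for a good response. No hypothesis test is planned. This stands as a limit on importance. Crossing the mark is not ruled out, though: a true slope of -0.05 with the same Rifafour slope and switch day gives -0.05 - 0.15 × 0.762/9 = -0.0627.
- **Reporting.** SAP Table 1.3 already summarises treatment discontinuations. That stands.

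**Conclusion.** The concern holds. The mismatch between label and data rule is explicit in both SAP sections and is there whether or not anyone switches. The bias is conditional: it needs a participant who stops GSK3036656, starts Rifafour, stays in the study, keeps giving sputum and is not replaced. It favours GSK3036656 only if Rifafour kills faster than the dose under study.

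On the assumed slopes, one switcher in nine after Day 4 to Day 8 overstates the arm slope by 3% to 48%, with about 10% in the middle case. In that case the shift is well below one standard error. If the 50% note does reassign switchers, only switches after Day 7 or later remain: 3.5% to 30% after Day 7, and less for later switches. No size was worked out for TTP, the other CFU periods or Model 2, where the same data rule applies. This should be fixed but is not fatal to the design.

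**What to change.** In SAP 7.1.4 and 7.2.4, for the CFU and TTP analyses under Models 1 and 2:

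- After permanent discontinuation, use only sputum samples whose designated day (the day collection starts, footnote L) is on or before the day of the last randomised dose.
- For GSK3036656 participants, also exclude any sample whose collection starts after the first Rifafour dose. The earlier cut applies. It goes by dosing day, so no washout window is needed.
- State how temporary interruptions are handled.
- Keep the all-data rule as a sensitivity analysis.
- In SAP Section 4, state that the 50%-of-doses note does not reassign mid-study switchers in the efficacy population, and reconcile it with the as-randomised definition.
- Report how many participants start Rifafour before Day 14. Early stops are already in Table 1.3.

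Separately, Protocol 3.3.1 and 8.1.3 need reconciling on whether haematology stops are study withdrawals, because that decides who can contribute data after stopping.

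Relabelling the effect as treatment policy would remove the contradiction but leave any Rifafour effect in the primary slope, which does not fit the primary objective.

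The cost is SAP wording and one flag built from dosing times already recorded. A stop after Day 6 loses 4 of that participant's 10 time points. The remaining days (0, 1, 2, 3, 4, 6) have a sum of squares of 66 - 16²/6 = 23.3. With one of nine cut, the slope information kept is (8 × 210 + 23.3)/(9 × 210) = 90%. The arm's standard error therefore rises by a factor of 1/√0.90 = 1.05, treating errors as independent.

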#### **7.1.5. Statistical Analyses / Methods**

Details of the planned displays are provided in [Appendix 10](#): List of Data Displays and will be based on GSK data standards and statistical principles.

Unless otherwise specified, endpoints / variables defined in Section [7.1.1](#) will be summarised using descriptive statistics, graphically presented (where appropriate) and listed.

**7.1.5.1. Statistical Methodology Specification**

Endpoint

 
• Rate of change in log10CFU per ml direct respiratory sputum samples over the period baseline to Day 14.
 

Model Specification

Model 1:
 
 
• Mixed model repeated measures analysis. Terms in the model:             
 
• Response: log10CFU
 
• Categorical: treatment
 
• Continuous: time, BMI
 
• Interaction: treatment*time
 
• Random: Subject
 
 
 
 
Model 2:
 
In addition, to characterize any bi-linear characteristics a bi- linear Bayesian regression model of the following form will also be fitted:
 $y_i = \begin{cases} \text{normal}(\alpha + \beta_1(t_i - cp), \sigma^2) & \text{if } t_i < cp \\ \text{normal}(\alpha + \beta_2(t_i - cp), \sigma^2) & \text{if } t_i \geq cp \end{cases}$ 
 
• Where cp=change (node) point as determined by the data (separate nodes for each treatment group), and t=time.
 
• The model will include terms for intercept, BMI, treatment, treatment*day before node, treatment*day after node, subject.
 
• This model would utilize uninformative uniform priors for cp and <math>\sigma^2</math> (discrete uniform(2,13) and uniform(0,5) respectively) and uninformative normal priors for the intercept, treatment, baseline log10CFU and BMI (normal(0,var=1000000)). Subject will be a random effect with an uninformative prior (normal(0,var), where var=uniform(0,5)).
 
• The efficacy population will be used for both models.
 
• Data from the standard of care arm will be pooled for the analysis.
 
• Where CFU plate counts are Too Numerous To Count (TNTC) a value of 2500 should be imputed for both models.
 

Model Checking & Diagnostics

Model 1: Mixed model repeated measures analysis:
 
 
• An autoregressive 1 covariance structure will be used. In the event this fails to converge alternative covariance structures may be considered such as VC.
 
• The Kenward and Roger method for approximating the denominator degrees of freedom will be used.
 
• Normality assumptions underlying the model used for analysis will be examined by obtaining a normal probability plot of the residuals and a plot of the residuals versus the fitted values (i.e. checking the normality assumptions and constant variance assumption of the model respectively) to gain confidence that the model assumptions are reasonable.
 

 
If there are any departures from the distributional assumptions, alternative models will be explored using appropriate transformed data (e.g. square root).
 
 
Model 2: Bi-linear Bayesian regression model:
 
 
The convergence will be examined using trace plots: All chains' trace plots will be inspected visually, to assess the mixing of each chain. Convergence is indicated when all chains appear to be mixing well and overlapping each other randomly (no chain's convergence is indicated until the chains of all model parameters appear well-mixed).
 
Additional convergence diagnostics, such as Monte Carlo Standard Error divided by the standard deviation of the posterior distribution (MCSE/SD), Gelman-Rubin statistic, effective sample size (ESS) and autocorrelation plots may also be reviewed.
 
The modelling will be subject to independent quality control. The final parameter estimates for the mean slopes and the mean node point should be within two times the Monte Carlo Standard Error (2xMCSE).
 

Model Results Presentation
 
 
Model 1: Summary of the mean daily rate of change, standard deviation and associated 95% confidence interval will be presented for each treatment arm.
 
Model 2: The mean and 95% highest posterior density (HDP) interval of the node, slope parameter before node and slope parameter after node, will be presented for each treatment arm.
 

Subgroup Analyses
 
 
No subgroup analyses are planned for this endpoint.
 


Sensitivity and Supportive Analyses
 
 
A sensitivity analysis will be performed (Model 1 only) excluding participants who withdraw from the study before Day 10 and/or who were replaced during the study.
 
Additional covariates (see Section 5.3) will be investigated in an exploratory manner using a mixed model repeated measures analysis. Each covariate will be investigated separately utilizing the model described for the primary endpoint. First the primary endpoint model will be fitted but including the covariate of interest and then the primary endpoint model will be fitted including both the covariate and treatment-by-covariate interaction.
 

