
 
• Rate of change in <math>\log_{10}</math>CFU per ml direct respiratory sputum samples over the period Day 2 to Day 14.
 
• Rate of change in time to sputum culture positivity (TTP) over the time period baseline to Day 14 (EBA TTP0-14)
 
• Rate of change in time to sputum culture positivity (TTP) over the time period Day 2 to Day 14 (EBA TTP2-14)
 

Model Specification

 
• As described for the primary endpoint, see Section 7.1.5, except: 
 
○ For the models for Days 2-14, baseline <math>\log_{10}</math>CFU (or baseline TTP for TTP (2-14) should be included as a continuous covariate.
 
 
 
• For the TTP endpoints, the data may be log transformed using base 10 if the residuals do not follow a normal distribution.
 

Model Checking & Diagnostics

 
• As described for the primary endpoint, see Section 7.1.5.
 

Model Results Presentation

 
• As described for the primary endpoint, see Section 7.1.5.
 

Subgroup Analyses

 
• No subgroup analyses are planned for these endpoints.
 

Sensitivity and Supportive Analyses

 
• No sensitivity or supportive analyses are planned for these endpoints.
 

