12.10.5. Efficacy Tables

Efficacy: Tables					
No.	Population	IDSL / Example Shell	Title	Programming Notes	Deliverable
CFU					
2.1.	Efficacy	Non-standard EFF_T1	Summary Table of log 10 CFU Counts Over Time		DE, SAC
2.2.	Efficacy	Non-standard EFF_T1	Summary Table of Change from Baseline in log 10 CFU Counts Over Time	Include baseline row similar to LB1 template.	DE, SAC
2.3.	Efficacy	Non-standard EFF_T2	Rate of Change in log 10 CFU by Treatment – Mixed Model Analysis	For dose escalation analysis, calculate EBA CFU(0-14) only. Supportive SAS output to be produced and archived	DE, SAC
2.4.	Efficacy	Non-standard EFF_T3	Node and Slope Parameter Estimates for log 10 CFU by Treatment – Bi-linear Bayesian Model Analysis	For dose escalation analysis, calculate EBA CFU(0-14) only. Supportive SAS output to be produced and archived	DE, SAC
2.5.	Efficacy	Non-standard EFF_T2	Rate of Change in log 10 CFU by Treatment – Mixed Model Analysis – Withdrawn/Replaced Participants Excluded	For endpoints CFU(0-14) and CFU(2-14) only. Supportive SAS output to be produced and archived	SAC
2.6.	Efficacy	Non-standard EFF_T4	Summary of Covariate and Treatment*Covariate Interaction Significance For log 10 CFU(0-14) Mixed Model Analysis	Supportive SAS output to be produced and archived	SAC
TTP					
2.7.	Efficacy	Non-standard EFF_T1	Summary Table of TTP Counts Over Time		SAC

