**CONFIDENTIAL**

201214

2.8.	Efficacy	Non-standard EFF_T1	Summary Table of Change from Baseline in TTP Counts Over Time	Include baseline row similar to LB1 template.	SAC
2.9.	Efficacy	Non-standard EFF_T2	Rate of Change in TTP –Mixed Model Analysis	Supportive SAS output to be produced and archived	SAC
2.10.	Efficacy	Non-standard EFF_T3	Node and Slope Parameter Estimates for TTP by Treatment –Bi-linear Bayesian Model Analysis	For endpoint TTP(0-14) only. Supportive SAS output to be produced and archived	

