Example : EFF\_T3  
 Population : Efficacy

Table EFF\_T3  
 Node and Slope Parameter Estimates for log10CFU by Treatment - Bi-linear Bayesian Model Analysis

Endpoint (units)	Treatment	N	n	Mean (95% HPD Interval)		
				Node	Slope Before Node	Slope After Node
EBA CFU 0-14 (log 10 CFU/mL)	<Rifafour>	xx	xx	x.xxx (x.xxx, x.xxx)	x.xxx (x.xxx, x.xxx)	x.xxx (x.xxx, x.xxx)
	<656 Dose 1>	xx	xx	x.xxx (x.xxx, x.xxx)	x.xxx (x.xxx, x.xxx)	x.xxx (x.xxx, x.xxx)
	<656 Dose 2>	xx	xx	x.xxx (x.xxx, x.xxx)	x.xxx (x.xxx, x.xxx)	x.xxx (x.xxx, x.xxx)
	<656 Dose ...>	xx	xx	x.xxx (x.xxx, x.xxx)	x.xxx (x.xxx, x.xxx)	x.xxx (x.xxx, x.xxx)
	<656 Dose 5>	xx	xx	x.xxx (x.xxx, x.xxx)	x.xxx (x.xxx, x.xxx)	x.xxx (x.xxx, x.xxx)
EBA CFU 2-14 (log 10 CFU/mL)	<Rifafour>	xx	xx	x.xxx (x.xxx, x.xxx)	x.xxx (x.xxx, x.xxx)	x.xxx (x.xxx, x.xxx)
	<656 Dose 1>	xx	xx	x.xxx (x.xxx, x.xxx)	x.xxx (x.xxx, x.xxx)	x.xxx (x.xxx, x.xxx)
	<656 Dose 2>	xx	xx	x.xxx (x.xxx, x.xxx)	x.xxx (x.xxx, x.xxx)	x.xxx (x.xxx, x.xxx)
	<656 Dose ...>	xx	xx	x.xxx (x.xxx, x.xxx)	x.xxx (x.xxx, x.xxx)	x.xxx (x.xxx, x.xxx)
	<656 Dose 5>	xx	xx	x.xxx (x.xxx, x.xxx)	x.xxx (x.xxx, x.xxx)	x.xxx (x.xxx, x.xxx)

Bi-linear model including treatment, day, BMI and treatment-by-day before node and treatment-by-day after node as covariates. The Day 2-14 model also includes log baseline CFU as a covariate. Baseline (Day 0) is defined as the mean of Day -2 and Day -1; if data was available at only one of these timepoints then that value was used as baseline.

Example : EFF\_T4  
 Population : Efficacy

Table EFF\_T4  
 Summary of Covariate and Treatment\*Covariate Interaction Significance For log10CFU (0-14) Mixed Model Analysis

Terms in the Model	Numerator Degrees of Freedom	Denominator Degrees of Freedom	F-test	p-value
Age [1]	xx	xx	x.xx	0.xxx
Treatment*Age [1]	xx	xx	x.xx	0.xxx
Creatinine clearance [2]	xx	xx	x.xx	0.xxx
Treatment*creatinine clearance [2]	xx	xx	x.xx	0.xxx
...				

Primary model includes treatment, day, BMI and treatment-by-day as covariates.

[figure not shown]
[1] Primary model fitted first with age, then with age + age\*treatment

[2] Primary model fitted first with creatinine clearance, then with creatinine clearance creatinine clearance\*treatment

...

Example : EFF\_F1  
Population : Efficacy

Table EFF\_F1  
Line Graph of Mean log10CFU Over Time by Treatment

[figure not shown]

Programming note: Include 95% confidence intervals of the slopes.

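### For CFU Day 2-14, SAP Model 2 allows a node at Day 2, where no data inform the first slope, and it states no slope prior

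*SAP*

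**What the plan says.** - **Model.** SAP 7.1.5.1, Model 2, fits one slope to times before the node and another from the node onward, with "separate nodes for each treatment group". The node and residual-variance priors are "discrete uniform(2,13) and uniform(0,5) respectively", so the node may be any whole day from 2 to 13.
- **Other priors.** The SAP gives "uninformative normal priors for the intercept, treatment, baseline" log10CFU and BMI, each with variance 1,000,000. The two slopes are not in that list.
- **Carry-over to Day 2-14.** SAP 7.2.5.1 specifies this endpoint with the words "As described for the primary endpoint, see Section 7.1.5, except". The one structural exception begins "For the models for Days 2-14, baseline": baseline enters as a continuous covariate. The node range is not changed.
- **Planned output.** Shell EFF_T3 (SAP Appendix 11) has a CFU Day 2-14 block giving the node and both slopes for each arm. Its footnote says "The Day 2-14 model also includes log baseline CFU as a covariate". In SAP 12.10.5, Table 2.4 limits the window at dose escalation only ("For dose escalation analysis, calculate EBA CFU(0-14) only"), so the final table includes Day 2-14.
- **TTP.** Table 2.10 restricts its bi-linear model: "For endpoint TTP(0-14) only".

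**The concern.** A change-point model needs data on both sides of every node that its prior allows. The range 2 to 13 meets this for Day 0-14, where baseline and Day 1 precede node 2. It does not for Day 2-14, where baseline has become a covariate and Day 2 is the first response. At node 2 the first slope drops out of the likelihood and its posterior is its prior.

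There is a second effect. Under a diffuse slope prior, every later node is penalised for having a first slope to estimate, and node 2 is not. The posterior is therefore drawn toward the node at which the reported slope means nothing. At stake are two of the three columns in one block of the final efficacy output.

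**Working it through.** No figure in the plan covers this point, so there is none to reproduce.

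**Step 1: sampling days on each side of the node.** Sputum days come from SAP Appendix 2, footnote l: daily to Day 4, then Days 6, 8, 10, 12 and 14.
- Day 2-14 responses: 2, 3, 4, 6, 8, 10, 12, 14. Node 2 has 0 days before and 8 from the node onward; node 3 has 1 and 7; node 4 has 2 and 6; node 12 has 6 and 2; node 13 has 7 and 1.
- Day 0-14 responses add baseline (Day 0) and Day 1, so node 2 has 2 and 8.

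**Step 2: why the posterior moves to node 2.** P(node=c | data) is proportional to (1/12) × m(c), where m(c) is the likelihood averaged over the priors. At c=2 averaging over the first slope contributes a factor of 1. At c≥3 it contributes roughly s/τ times any gain in fit, where s is the standard error of that slope and τ its prior SD. Taking s from the restricted-node fit in step 4 (n=9, linear data): s ≈ 0.194/3.92 ≈ 0.05. With τ = 1000, s/τ ≈ 1/20,000. Eleven such nodes total about 11/20,000 ≈ 0.0006, so P(node=2) is near 0.999. At node 2 the 95% interval for the first slope is the prior's: 2 × 1.96 × 1000 = 3,920.

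**Step 3: simulation of one arm.** Assumed, because the SAP does not give them: residual SD 0.4, participant SD 0.8 (log10 CFU), slope-prior SD 1000, 10 or 1 (variance 1,000,000, 100 or 1). BMI and baseline are omitted; 60 data sets per setting. Cells show median P(node=2), with the median 95% interval width for the first slope in brackets.

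| True daily slope | n | Prior SD 1000 | Prior SD 10 | Prior SD 1 |
|---|---|---|---|---|
| -0.06 throughout | 9 | 0.998 (3,910) | 0.870 (37.8) | 0.400 (3.06) |
| -0.06 throughout | 15 | 0.999 (3,910) | 0.906 (38.3) | 0.488 (3.25) |
| -0.12, then -0.04 from Day 6 | 9 | 0.997 (3,910) | 0.708 (36.1) | 0.303 (2.76) |
| -0.12, then -0.04 from Day 6 | 15 | 0.997 (3,910) | 0.796 (37.2) | 0.230 (2.48) |
| -0.25, then -0.03 from Day 6 | 9 | 0.768 (3,680) | 0.047 (0.817) | 0.003 (0.297) |
| -0.25, then -0.03 from Day 6 | 15 | 0.034 (0.526) | 0.000 (0.214) | 0.000 (0.228) |

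A second set used SDs 0.5 and 1.0 and reports means. At variance 1,000,000, P(node=2) is 0.996-0.998 for linear data, 0.94-0.98 for a mild bend, and 0.71, 0.43 and 0.13 at n = 9, 15 and 25 for the steep bend (-0.25 then -0.03). For linear or mildly bent data it is about 0.63-0.87 at variance 100 and 0.20-0.45 at variance 1.

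**Step 4: comparisons at prior SD 1000 (SDs 0.4 and 0.8).**
- Day 0-14, linear data: P(node=2) is about 0.09-0.12, close to the prior 1/12 = 0.083; interval width 0.12-0.15. The cause is therefore the window combined with the node range.
- Day 2-14 with the node limited to 4-12: interval width 0.15-0.26 over all scenarios. With linear data the posterior mean node is 7.9-8.0, the centre of the restricted prior.

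**The case against.** **The size rests on a prior that the SAP does not give.** A reader might infer that the collapse follows from the stated node prior. It does not: that prior alone gives node 2 a probability of 1/12. The collapse needs a diffuse slope prior, and 1,000,000 is borrowed from the other terms. This stands, and it makes the missing slope prior part of the finding. What does not depend on it is that node 2 is allowed and has no earlier data.

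**A real bend can be found.** A reader might infer that the Day 2-14 node and first slope are meaningless in every arm whatever the data. The steep-bend rows contradict this. At n=15 and prior SD 1000 the median posterior mean node is 5.4 and the first slope is recovered at -0.24. The pooled standard-of-care arm could be larger still (Protocol 10.1.1 originally expected about 25). This stands, with the caution that 48% of those n=15 data sets still put more than 5% on node 2.

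**The consequence is limited and visible.** SAP 2.1 calls Model 2 supportive, CFU Day 2-14 is a secondary endpoint, no formal hypothesis test is planned, and the block is absent from dose-escalation output. An interval of about 3,900 log10/day would be obvious on the page. All of this stands. The planned checks need not flag the fault, however. Draws from a prior can mix well, and with, say, 10,000 effective draws and a posterior SD near 1000 the Monte Carlo error is 1000/√10,000 = 10, so the tolerance of twice that error in SAP 7.1.5.1 is 20 log10/day. With a tighter slope prior the interval would also look less absurd.

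**Conclusion.** The concern holds in conditional form. Following the SAP as written, the CFU Day 2-14 node and slope before the node are usually prior-driven when the data are linear or mildly bent and the slope prior is very diffuse: P(node=2) is about 0.94-0.999 over the two sets of assumed SDs. Over the same settings it is about 0.63-0.91 at slope variance 100 and 0.20-0.49 at variance 1. A flat improper slope prior would be worse, since the first slope would have no proper posterior at node 2.

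The documents do not support saying that every arm is affected whatever the data, or that the node prior alone is the cause. The slope after the node stays estimable, although at node 2 it is simply the overall Day 2-14 slope. Model 1, bi-linear CFU Day 0-14 and bi-linear TTP Day 0-14 are untouched. The structural gap is certain from the text; its size depends on the assumed SDs and slope prior. It is worth correcting before the final analysis but does not threaten the primary result.

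**What to change.** Preferred: remove the CFU Day 2-14 block from shell EFF_T3, and state in SAP 7.2.5.1 and in the note to Table 2.4 that Model 2 is fitted to CFU Day 0-14 only, matching Table 2.10 for TTP. The same sentence in 7.2.5.1 should confine Model 2 to Day 0-14 for TTP, because at present only the Table 2.10 note does so. State the slope prior for the Day 0-14 model. Model 1 still reports CFU Day 2-14 in EFF_T2, so no endpoint loses its estimate.

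If the block is kept: restrict the Day 2-14 node to 4-12, which leaves at least two sampling days on each side, and state the slope prior. Add a note that this makes the first slope estimable but leaves the node near the centre of its prior when there is no real bend.

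The cost is a few lines of SAP text and one shell. Dropping the block reduces programming, and neither option changes data collection.
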